Secondary objectives: Compare trajectories of suicidal ideation, NSSI, depression, and anxiety; evaluate feasibility/acceptability; explore predictors and moderators of response (e.g., prior attempts, sex, age, symptom severity).

Hypotheses

1. BCBT will yield a lower hazard of suicide attempt (superiority).

2. BCBT and ST will show similar improvements in general anxiety/depression, but BCBT will outperform ST on suicide-related outcomes.
3. BCBT will demonstrate high feasibility and acceptability in this population, as reflected by satisfactory recruitment rates, session attendance, treatment adherence, and positive patient satisfaction ratings.
4. Baseline characteristics, including history of prior suicide attempts, baseline symptom severity, age, and sex, will be associated with differential clinical outcomes over follow-up.

Methods

Trial Design

Single-site, parallel-group, superiority RCT (1:1) with blinded outcome assessment and 6-month follow-up. The protocol follows the SPIRIT 2025 guidelines; reporting will follow the CONSORT 2025 guidelines and the extensions for non-pharmacological interventions and harms.

Randomization

Participants will be randomly assigned in a 1:1 ratio, stratified by sex and prior suicide attempt, using a computer-generated permuted-block randomization sequence with variable block sizes (blocks of 4 and 6) to prevent allocation prediction. The sequence will be generated by an independent researcher with no involvement in participant recruitment or outcome assessment, using validated statistical software. Participants will be enrolled by the study coordinator; treatment allocation will be released only after eligibility is formally confirmed and informed consent is obtained. Allocation concealment will be maintained through a centralized, web-based randomization module within REDCap, which withholds the assigned arm until the enrollment step is completed and locked. Neither the enrolling clinician nor the participant will have access to forthcoming allocations.

Blinding

Given the nature of psychotherapy research, blinding of participants and therapists to treatment allocation is not feasible (Cuijpers et al., 2015). However, all outcome

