assessors (blinded evaluators) will be masked to treatment assignment throughout the study. Blinded evaluators are trained research assistants with no involvement in treatment delivery or session documentation. Participants will be instructed at enrollment not to disclose their treatment condition during assessment visits, and assessments will be conducted in a separate physical or virtual space from therapy rooms. Blinded evaluators will not have access to session notes, therapist logs, or any allocation-linked material. Blinding integrity will not be formally assessed; however, procedures to minimize unblinding include instructing participants not to disclose their treatment condition, conducting assessments in settings separate from therapy sessions, and restricting blinded evaluators' access to treatment-related materials.

Study setting

Institute of Psychiatry of the Hospital das Clínicas, Faculty of Medicine, University of São Paulo, is the selected study site for this randomized controlled trial.

Eligibility criteria

a. Inclusion:

1. Age 18–65 years.
2. Treatment-seeking outpatient or recent psychiatric inpatient discharge ≤ 30 days.
3. Current suicidal ideation during the past week and/or suicide attempt within the past month.
4. Ability to consent and communicate in Brazilian Portuguese.

b. Exclusion:

1. Acute psychosis or mania precluding psychotherapy participation.
2. Substance intoxication/withdrawal requiring stabilization.
3. Immediate need for inpatient admission at screening.

4. Severe cognitive impairment/neurocognitive disorder; moderate–severe intellectual disability.
5. Inability to attend visits or lack of reliable contact for safety monitoring.

Training, Supervision, and monitoring of study clinicians

Two clinicians will be assigned to provide both groups' treatments. Training will consist of sessions with didactic instruction, live supervised role plays with feedback, assigned reading materials, and supervision throughout the process. The main reference will be the BCBT manual, elaborated by Rudd & Bryan (2018), which contains clinical practice guidelines. To enhance the treatment credibility, fidelity checklists will be used and checked upon supervision by the researchers.

Concomitant Treatments

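### The protocol prints the block sizes (4 and 6) that are meant to prevent prediction, so someone with complete ordered records of past arms could deduce a few allocations with certainty

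*Protocol*

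**What the plan says.** Protocol, Randomization: "Participants will be randomly assigned in a 1:1 ratio, stratified by sex and prior suicide attempt", by computer-generated permuted blocks of varying size, given as "blocks of 4 and 6) to prevent allocation prediction". An independent researcher without a part in recruitment or outcome assessment generates the sequence. "Participants will be enrolled by the study coordinator", and the arm is released through a central REDCap module "which withholds the assigned arm until the enrollment step is completed and locked". The section adds that neither the enrolling clinician nor the participant can see forthcoming allocations.

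Three other places bear on how much of the past sequence staff can know:

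- Trial Design: "Single-site, parallel-group, superiority RCT (1:1) with blinded outcome assessment and 6-month follow-up".
- Blinding: "blinding of participants and therapists to treatment allocation is not feasible".
- Training, Supervision, and monitoring of study clinicians: "Two clinicians will be assigned to provide both" treatments.

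Author Contributions lists some authors both for clinical delivery and for methodology and the statistical plan. Some people who know the block sizes therefore also treat participants.

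**The concern.** Varying the block size protects against prediction only while the end of a block cannot be located. Printing both sizes in the document the team works from gives away part of that protection. Central release answers a different threat, namely sight of the list. It does nothing about deduction from arms already assigned, and in this trial each arm becomes known to the therapist and the participant once treatment begins. Between them, the two clinicians learn every arm that is delivered.

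What is at stake is selection bias. Some exclusions under Eligibility criteria call for judgement before allocation, such as an immediate need for admission or psychosis severe enough to preclude psychotherapy. If the person making that judgement, or deciding when to enrol, knew the next arm, the two groups could differ at baseline in ways that randomization should have ruled out.

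**Working it through.** The protocol gives no figure for predictability, so there is none to reproduce.

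**Inputs from the protocol.** Block sizes 4 and 6; 1:1 ratio; four strata (sex by prior attempt); N = 150.

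**Assumptions, because the protocol does not give them.** Equal chance of the two sizes (varied from 20% to 67% blocks of 6); strata of 38, 37, 38 and 37 (70, 30, 35 and 15 gave nearly the same results).

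**Step 1: why certainty arises.** A block of 4 holds two of each arm. If three of the first four places in a stratum go to one arm, the opening block must be of size 6 and its remaining places must all go to the other arm. A block of 6 has C(6,3) = 20 orderings. Those with all three of one arm in the first four places number 2 × C(4,3) = 8. So 8/20 = 40% of opening blocks of 6 give themselves away. With equal mixing this is 0.5 × 0.40 = 20% of strata, and 1 − 0.8^4 = 59% of trials have at least one such stratum at its opening block.

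**Step 2: the whole trial.** Simulate sequences of 150. Give a tracker the possible sizes and every past arm in order within stratum, and update by Bayes' rule the probabilities of the current block size and position. Count an allocation as certain when its predictive probability is 0 or 1.

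| Tracker's knowledge | Block mix (4 : 6) | Mean certain of 150 | Trials with at least one |
|---|---|---|---|
| All past arms, sizes 4 and 6 known | 50 : 50 | 8.5 (5.7%); 5th to 95th percentile 2 to 17 | 97% |
| Same | 80 : 20 | 3.6 (2.4%) | 78% |
| Same | 33 : 67 | 11.1 (7.4%) | 99% |
| 90% of arms seen, gaps recognised | 50 : 50 | 5.3 (3.5%) | not reported |
| Random half of arms seen, order and count of all entries known | 50 : 50 | 0.4 (0.3%) | not reported |
| All past arms, but a size of 8 must also be allowed for | 50 : 50 | 0 | 0% |

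Repeat simulations of the first row gave 5.4% to 5.8%, that is, about 8 to 9 allocations.

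**Step 3: what disclosure adds.** With full knowledge of past arms, the best guess is right about 69% of the time, against 50% by chance. The figure is the same when the tracker must also allow for a size of 8, because the best guess is then still the arm that is behind. Disclosure therefore moves the certain share from 0 to about 6% and leaves the guess rate unchanged.

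**Step 4: comparison.** Under the same full knowledge, a known fixed block of 4 makes about 32% of allocations certain and a fixed block of 6 about 24%. Varying the size already removes most of the certainty.

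**The case against.** The strongest reply has four parts.

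1. *Full knowledge is demanding.* The 5 to 6% needs every past arm, in exact order, in each of four strata. Neither therapist alone need see all participants, and a therapist who sees a random half can call almost nothing with certainty. With 90% of arms seen and the gaps unnoticed, about 31% of apparently certain calls are wrong. This stands, and it makes 5 to 6% an upper value under the equal-mix assumption.

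2. *No route to bias is documented.* A coordinator enrols, eligibility and consent come before release, and nothing says that therapists decide eligibility or that the coordinator reviews cumulative arms by stratum. This stands as a limit. The protocol does not exclude the route either: it uses both a study coordinator and an enrolling clinician, and does not say that either is separate from the therapists or that the sizes are kept from them.

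3. *Most predictability comes from small blocks in an open-label trial, not from printing the sizes.* This is correct, as the unchanged 69% shows. It limits the gain but does not remove it.

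4. *Silence on operational restrictions is not an error.* That is true of silence. Here, however, the protocol states a design detail that works against the purpose it gives for it.

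A reader might infer that anyone who tracks past arms can foresee allocations, or that steering a few high-risk participants could move a result resting on about 17 events. The documents support neither. Simple tracking is not enough, and no calculation backs the second inference. At the protocol's 15% event rate, 8.5 certain places correspond to 8.5 × 0.15 ≈ 1.3 expected events before any selection, and steering would also need a suitable patient of the right stratum at the right moment.

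**Conclusion.** The point holds as a minor one. Publishing sizes 4 and 6 lets someone with complete, ordered, per-stratum knowledge deduce up to about 5 to 6% of allocations (roughly 8 of 150) with certainty under an assumed equal mix. The share is about 2 to 7% across the other mixes examined and close to 0% for someone who sees only half the arms. Bias would follow only if that person could also influence whom or when to enrol, which the protocol neither shows nor excludes. This is a weakened safeguard that is cheap to restore, and it is not evidence that concealment has failed.

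**What to change.** - In Randomization, replace the parenthesis that gives the sizes with wording such as: *randomly varying block sizes, known only to the independent sequence generator*.
- Keep the sizes in a restricted document that is not available to enrolling or treating staff.
- Because 4 and 6 are already disclosed, have the independent researcher use undisclosed sizes that differ from 4 and 6 alone for any part of the sequence not yet used. The protocol does not give recruitment status, so how much of the sequence this covers must be established first.

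The cost is one wording change and, where it applies, a new sequence file. If a larger block is included, slightly more imbalance is possible at the end of each of the four strata. The gain is the removal of certain predictions. Best-guess accuracy stays at about 69% if only the sizes are hidden, and would fall only with larger blocks.

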These outcomes will be assessed using the Beck Scale for Suicide Ideation (BSI) for suicidal ideation; the Columbia–Suicide Severity Rating Scale (C-SSRS) for suicidal ideation and behavior; the SAFER and SAFER Follow-Up scales for high-risk self-harm monitoring; the Beck Depression Inventory–II (BDI-II) and Montgomery–Åsberg Depression Rating Scale (MADRS) for depressive symptoms; the Generalized Anxiety Disorder-7 (GAD-7) for anxiety; the Patient Health Questionnaire-9 (PHQ-9) for depression severity; the Deliberate Self-Harm Inventory–short form (DSHI-s) for nonsuicidal self-injury; the Duke University Religion Index (DUREL) for religiosity; the Purpose in Life Test (PIL) for perceived meaning in life; the Subjective Happiness Scale (SHS) for subjective well-being; the Short-Form Health Survey-12 (SF-12) for health-related quality of life; the Hypomania Checklist-32 (HCL-32) for hypomanic symptoms; the PROMIS Sleep Disturbance instruments for sleep-related functioning; the NIH Brief Fatigue Inventory for fatigue (NIH - BFI); Fatigue Severity Scale (FSS) and the Suicide Cognitions Scale–Revised (SCS-R) for suicide-specific maladaptive cognitions. A sociodemographic and clinical scale developed by the authors will assess participants' demographic characteristics, psychiatric history, prior suicide attempts, treatment history, and current clinical status. See Table 2 in Supplementary Material for assessment schedule.

Beck Scale for Suicide Ideation (BSI)

The Beck Scale for Suicide Ideation (BSI), developed by Beck & Steer (1991), is a self-report scale designed to identify the presence of suicidal ideation and assess associated factors, including suicide plans, behaviors, and attitudes. The scale consists of 21 items, each with three possible responses, and is used to measure the intensity of suicidal thoughts (Beck & Steer, 1991). The BSI was translated and validated for the Brazilian population by Cunha (2001), with its psychometric properties found to be satisfactory in both clinical and non-clinical samples.

Beck Depression Inventory–II (BDI-II)

The BDI-II is a 21-item self-report inventory assessing depressive symptom severity over the previous two weeks. Items cover cognitive, affective, and somatic features

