ranked secondary analyses; the PHQ-9 provides a brief screening complement and the MADRS a clinician-rated perspective sensitive to change. Similarly, the NIH-BFI offers a multi-dimensional clinician-rated fatigue assessment, while the FSS captures subjective functional impairment. Instruments measuring religiosity (DUREL), quality of life (SF-12), hypomanic symptoms (HCL-32), sleep (PROMIS), meaning in life (PIL), and subjective well-being (SHS) are included for descriptive and exploratory purposes and are not part of the ranked secondary outcome hierarchy. Assessment burden was considered during protocol development; instruments are administered in a fixed, piloted order, and estimated completion time per assessment visit does not exceed 60 minutes.

Sample size and power

We power the primary analysis (time-to-first attempt) using Schoenfeld's method for Cox models [32]. Assuming a hazard ratio (HR) = 0.50 (BCBT vs ST), two-sided $\alpha=0.05$, and 80% power, the number of required events is:

$$E=[\ln(HR)]^2(Z_{1-\alpha/2}+Z_{1-\beta})^2$$

If the overall 6-month event rate is ~15% in this high-risk sample (e.g., 20% ST vs 10% BCBT), then $N \approx 113$ would be required to accrue ~17 events. To accommodate 25% attrition, we plan $N=150$ (75 per group), yielding $\geq 80\%$ power under these assumptions. This sample also provides $\geq 80\%$ power to detect small-to-moderate between-group effects (e.g., standardized mean difference $d \approx 0.38$) on continuous secondary outcomes with repeated measures.

Statistical analysis plan

- Principles: Intention-to-treat primary; $\alpha=0.05$, two-sided; 95% CIs. Time zero is defined as the date of randomization. Follow-up begins at randomization and continues until first suicide attempt, death, withdrawal of consent, or administrative censoring at the 6-month assessment, whichever occurs first. Any suicide attempt occurring after eligibility screening but before

randomization will be documented as a baseline clinical event but will not count as a primary outcome event; this ensures that the risk period is aligned comparably across both arms from the moment of allocation.

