- Primary analysis: Cox model estimating HR for BCBT vs ST, adjusting for stratification factors (sex, prior suicide attempt), with additional covariates (age and baseline suicidal ideation) included in sensitivity analyses. Check proportional hazards (Schoenfeld residuals); if violated, use time-varying effects or restricted mean survival time. Given approximately 17 anticipated events, including four covariates yields an events-per-variable (EPV) ratio of ~4, below the commonly recommended threshold of 10. To reduce the risk of overfitting, the pre-specified primary model will include only the two stratification factors (sex and prior suicide attempt) as covariates (EPV ~8.5). Adjustment for age and baseline suicidal ideation will be conducted as a supplementary sensitivity analysis.
- Secondary analyses: Linear mixed-effects models (random intercepts) for fixed effects: time, group, group×time; GEE/logistic models for binary outcomes (e.g., any NSSI).
- Missing data: Missing At Random (MAR) is defined as missingness that depends only on observed data; Missing Not At Random (MNAR) refers to missingness that depends on unobserved data (e.g., patients drop out because their suicidal ideation worsened). Time-to-event outcome: participants lost to follow-up will be censored at the date of last confirmed contact. Sensitivity analyses will include: (a) best-case scenario—all BCBT dropouts are assumed attempt-free (censored at day 180) while all ST dropouts are assumed to have attempted at their last contact date; (b)

worst-case scenario—the reverse; (c) tipping-point analysis—identifying the minimum assumed increase in hazard for censored BCBT participants that renders the primary result non-significant.

- Exploratory moderators (hypothesis-generating only): These analyses are explicitly exploratory. Given the projected sample size and anticipated number of primary events, treatment-by-baseline interaction tests are underpowered for definitive subgroup inference and must not be interpreted as confirmatory evidence of effect heterogeneity. Interactions of treatment with baseline factors (e.g., prior attempt, sex, age, baseline symptom severity) will be examined with marginal effects and graphical probes. Mediation (e.g., change in cognitive distortions) may be explored descriptively if data allow. All findings will be framed as generating hypotheses for future adequately powered trials.

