- Multiplicity: The primary outcome (time-to-first suicide attempt) is the sole pre-specified confirmatory endpoint, tested at two-sided $\alpha=0.05$. Secondary outcomes are organized in the following interpretive hierarchy: (1) suicidal ideation (BSI, C-SSRS ideation subscale); (2) non-suicidal self-injury (DSHI-s); (3) depressive symptoms (BDI-II); (4) anxiety (GAD-7); (5) treatment feasibility and acceptability. No formal α -adjustment is planned across secondary outcomes; results should be interpreted in light of the number of comparisons made and regarded as exploratory. Exploratory moderator and mediator analyses carry no inferential weight regarding treatment efficacy and will be clearly labelled as hypothesis-generating throughout the manuscript.

Data capture and management

REDCap with role-based access, audit trails, range checks, and encrypted storage. Identifiers stored separately; audio files on secure institutional servers. Only authorized personnel access identifiable data.

Monitoring and safety

Independent Data and Safety Monitoring Board (DSMB) reviews SAEs quarterly (or ad hoc) and may recommend protocol modifications or early termination for safety. AEs/SAEs reported to CEP/CONEP per Brazilian regulation. Participants receive 24/7 emergency contacts.

Discussion

The BCBT-BR trial rigorously evaluates whether suicide-specific CBT confers advantages over common-factor ST in a Brazilian outpatient setting. Strengths include an active comparator, blinded assessment, event-focused primary outcome, therapist cross-training with fidelity checks, and cultural adaptation. Findings will guide scalable implementation of suicide-focused care in LMIC public mental health systems.

Ethics and Registration

Ethics: CONEP/Plataforma Brasil approval CAAE 88755725.9.0000.0068

Registration: ClinicalTrials.gov [registration pending; CAAE 88755725.9.0000.0068 refers to the Brazilian ethics approval (CONEP/Plataforma Brasil) and is reported separately above] 88755725.9.0000.0068

Protocol amendments: Any substantial changes will be submitted to ethics committees and updated in registries.

Funding

There is no funding for this trial. RFD receives scholarship from São Paulo Research Foundation (FAPESP) (#2024/10058-0).

Author Contributions

- Conceptualization: [name] (LB), [name] (RFD), [name] (ECM), [name] (CB)
- Methodology: LB, [name] (RERF), CB, RFD

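### The random-intercepts-only model for the continuous secondary outcomes, without baseline adjustment, understates the error of group×time and wastes power; for suicidal ideation, entry criterion 3 makes this worse

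*Protocol*

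**What the plan says.** In the Protocol, Statistical analysis plan, the Secondary analyses item gives the continuous-outcome model as "Linear mixed-effects models (random intercepts) for fixed effects: time, group, group×time". No baseline score or stratification factor is among the terms. Baseline suicidal ideation is named as a covariate only for a sensitivity version of the Cox model.

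The Multiplicity item puts "1) suicidal ideation (BSI, C-SSRS ideation subscale" at the top of the secondary hierarchy. It plans no alpha adjustment for secondary outcomes and asks that they be read as exploratory.

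Eligibility criteria, inclusion item 3, is "Current suicidal ideation during the past week and/or suicide attempt within the past month". Either route suffices, and no minimum BSI score is set. The Protocol describes the BSI as a scale that "is used to measure the intensity of suicidal thoughts", and says it also covers plans, behaviors and attitudes.

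Sample size and power claims at least 80% power for a standardized difference of about 0.38 on continuous secondary outcomes, with 75 per group and 25% attrition. The Abstract lists five assessment times; Table 2 in the Supplementary Material marks the BSI at T0 to T15, which is 16.

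**The concern.** A random-intercept model lets patients differ in level but not in rate of change. If rates do differ, the model treats that variation as visit-to-visit noise and averages it away over visits. The standard error of group×time is then too small, so confidence intervals are too narrow and the test rejects too often.

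Criterion 3 adds a reason to expect different rates on the ideation scale. A patient who entered on an attempt alone probably starts low and stays flat, while a patient with ideation tends to decline. Separately, group×time with baseline among the repeated measures is a difference in change. It does not use the correlation between baseline and follow-up as efficiently as adjustment does.

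At stake is the ideation part of Hypothesis 2, that BCBT outperforms supportive therapy on suicide-related outcomes.

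**Working it through.** **1. The plan's own power figure.** With d = 0.38 and 75 per arm, a plain comparison has power Φ(0.38×√(75/2) − 1.96) = Φ(0.37) = 64%. For 80%, 2×(1.96 + 0.84)²/0.38² gives 109 per arm. To reach 80% with 75, the variance must fall to 75/109 = 0.69 of its value, for example by baseline adjustment with correlation √(1 − 0.69) = 0.56. With 56 completers per arm the correlation must be about 0.70. The Protocol gives no correlation, so the figure is attainable but cannot be verified.

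**2. Why the standard error is too small.** Take m visits, Sxx the sum of squared deviations of visit time, σ² the residual variance, and v the variance of individual slopes.
- True variance of one patient's slope: σ²/Sxx + v.
- Variance the random-intercept model uses: σ²/Sxx + v/(m − 1).

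If a share p stays flat at zero and the rest decline by 8 points on average with slope SD τ, then v = (1 − p)τ² + p(1 − p)×8², and the mean residual variance is (1 − p)σ².

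Assumed inputs (none is in the Protocol): weeks 0, 6, 12, 18, 26 scaled to 0–1, so Sxx = 0.608; σ = 4; τ = 3; linear time. The 75 per arm is from the Protocol.

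| | p = 0 | 20% | 40% |
|---|---|---|---|
| (1 − p)σ²/Sxx | 26.30 | 21.04 | 15.78 |
| v | 9.00 | 17.44 | 20.76 |
| True variance | 35.30 | 38.48 | 36.54 |
| Model variance | 28.55 | 25.40 | 20.97 |
| Model SE / true SE | 0.90 | 0.81 | 0.76 |
| Type I error, 2Φ(−1.96×ratio) | 7.8% | 11.1% | 13.8% |
| Simulated, scores bounded at 0: SE ratio | 0.91 | 0.83 | 0.76 |
| Simulated type I error | 7.6% | 10.9% | 13.5% |

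With 16 visits, as Table 2 reads, the simulated type I error is 11.7%, 18.0% and 24.7%. A standard error that allows random slopes holds 4.6 to 5.5%.

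Two checks on the cause:
- With p = 0 and τ = 5, the true variance is 26.30 + 25 = 51.30 and the model's is 26.30 + 6.25 = 32.55, a ratio of 0.80 with no low scorers at all.
- The true SE, √(2×variance/75), is 0.97, 1.01 and 0.99 across the table. It barely moves with p.

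**3. What baseline adjustment adds.** Assumed: 150 analysed, four post-baseline visits; patients with ideation at mean BSI 17 at baseline and 10 at follow-up under supportive therapy; between-patient SD 5.5, within-patient SD 5; effect 0.38×7.5 = 2.85 points in patients with ideation only; the others stay near 0. Simulated results, with the effect averaged over follow-up unless stated:

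| Share of low scorers | 0 | 10% | 20% | 30% |
|---|---|---|---|---|
| Type I error, planned model | 6% | 8% | 10% | 11% |
| Type I error, baseline-adjusted | 5–6% | 5–6% | 5–6% | 5–6% |
| Power, planned model | 83% | 73% | 68% | 59% |
| Power, baseline-adjusted | 97% | 95% | 93% | 88% |
| Power, baseline-adjusted, one visit only | 78% | 72% | 70% | 61% |

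Repeat runs moved type I error by up to about 1.4 points and power by up to about 4 points.

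**4. Where the power goes.** The average effect is diluted to 2.85×(1 − p) = 2.85, 2.57, 2.28 and 2.00 points. The planned model's power is also flattered by its small standard error. The same change contrast with a valid standard error has power 78%, 66%, 54% and 41%, at 4.4 to 5.4% type I error. Repairing the covariance alone therefore corrects the error rate but does not recover power.

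**The case against.** A reader might infer that criterion 3 is itself a mistake. The documents do not support that. The primary outcome is time to first suicide attempt, for which recent attempters are a natural target. The understated error comes from the random-intercepts-only structure and appears without any low scorers once slopes differ.

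A reader might also infer that low scorers make the planned estimate itself less precise. In general they do not: its true standard deviation under the null stayed at about 0.91 from 0 to 30% in the second scenario.

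Other points stand in part:
- The low baseline is an inference. Because the BSI also covers plans, behaviors and attitudes, an attempter without past-week ideation need not score zero, and can worsen.
- The Protocol does not say that baseline is one of the repeated outcomes, how time is coded, or which contrast is tested. Reading group×time as a difference in change is the natural reading, not a stated one.
- Provided a past-month attempt counts as a prior attempt, all attempt-only entrants fall in the prior-attempt stratum, so stratification partly balances entry route. Patients with ideation and an older attempt share that stratum. Any remaining imbalance is sampling variation, not bias.
- Comparing trajectories is a stated objective, and covariate lists are often left to a separate analysis plan. Here, however, the Protocol itself fixes the random-effects structure and the fixed effects.
- The exploratory label means no confirmatory claim is affected. It does not justify intervals that are too narrow.

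**Conclusion.** The point holds as a weakness of the secondary-outcome model, which criterion 3 aggravates for ideation. Under the assumed values, type I error is about 6 to 11% instead of 5% with four post-baseline visits, and higher if the BSI is analysed at all 16 occasions. Baseline adjustment raises power for the average over follow-up from 83% to 97% with no low scorers, and from 59% to 88% with 30%. The first of these gaps is the general advantage of adjustment and owes nothing to criterion 3. The fall along each row is largely dilution. These gains apply to the average over follow-up; a reader should not expect them at a single visit, where adjusted power is about 78% to 61%.

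The direction of the standard-error problem is secure whenever individual rates of change differ. Its size rests on BSI means, SDs, slope variation and a share of low scorers that the Protocol does not give. The primary analysis is untouched.

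**What to change.** Leave criterion 3 as it is and amend the Secondary analyses item:
- Model post-baseline scores with baseline score, baseline×visit, visit, group, group×visit, sex and prior suicide attempt.
- Use an unstructured covariance, or random slopes or robust standard errors. If all 15 post-baseline occasions in Table 2 are modelled, an unstructured matrix has 15×16/2 = 120 parameters, so one of the alternatives is more practical. State which visits enter the model.
- Report the between-group difference averaged over follow-up as the main contrast, with per-visit differences alongside.
- For the BSI, add past-week ideation at entry (yes/no) as a covariate, and a supportive analysis in patients with baseline ideation.
- For the C-SSRS ideation subscale, Table 2 as it reads in the available copy shows no T0 value. If none exists, use baseline BSI as the covariate.

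No new data are needed: the BSI is scheduled at T0, sex and prior attempt are used for stratification, and past-week ideation is assessed for eligibility. The cost is a few more model terms, a simple rule for missing baseline scores, and a result stated as a difference at follow-up rather than a difference in change.
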